- Derived criteria "Durability of Left atrial roof line at remap" will be defined as follows:
IF Left atrial roof line lesion durable ='Yes' in **Follow-up 3D electroanatomical mapping form (RM)** **THEN** Durability of Left atrial roof line at remap = 'Yes'
ELSE IF Left atrial roof line lesion durable ='No' in **Follow-up 3D electroanatomical mapping form (RM)** **THEN** Durability of Left atrial roof line at remap = 'No'
- Derived criteria "Durability of Left atrial Posterior line" will be defined as follows:
IF Left atrial Posterior line lesion durable ='Yes' in **Follow-up 3D electroanatomical mapping form (RM)** **THEN** Durability of Left atrial Posterior line at remap = 'Yes'
ELSE IF Left atrial Posterior line lesion durable ='No' in **Follow-up 3D electroanatomical mapping form (RM)** **THEN** Durability of Left atrial Posterior line at remap = 'No'
- Derived criteria "Therapeutic Success ON/OFF AAD" will be defined as follows:

CONFIDENTIEL / CONFIDENTIAL

Toute reproduction ou distribution, totale ou partielle, de ce document, sans autorisation préalable de ICON PLC est interdite.
Reproduction and distribution of this document, in whole or in part, is strictly forbidden without prior authorization from ICON PLC.

IF "AF/AFL/AT status"= 0 **AND** "RF touchup"= 0 **AND** "ABL >90 days" = 0 **in MDT excel file**
THEN therapeutic success='Yes'
ELSE therapeutic success='No'

- Derived criteria "Therapeutic Success Off ADD" will be defined as follows:
IF Therapeutic success ='Yes' **AND** Class I/III AAD>90days=0 **in MDT excel file** **THEN** therapeutic success Off ADD ='YES'
ELSE IF Therapeutic success ='No' **AND** Class I/III AAD>90days=0 **in MDT excel file** **THEN** **THEN** therapeutic success Off ADD ='NO'
- Derived criteria "Therapeutic Success On ADD" will be defined as follows:
IF Therapeutic success ='Yes' **AND** Class I/III AAD>90days=1 **in MDT excel file** **THEN** therapeutic success On ADD ='No'
Else If Therapeutic success ='No' **AND** Class I/III AAD>90days=1 **in MDT excel file** **THEN** **THEN** therapeutic success On ADD ='No'

Additional endpoints

- Derived criteria "Proportion of all ablated pulmonary veins that are isolated at the Index Procedure using the study device" will be defined as follows:
COUNT of [(Left Superior Isolated/Blocked ='Yes', Left Inferior Isolated/Blocked='Yes', Left Common Ostium Isolated/Blocked='Yes', Right Middle Isolated/Blocked='Yes', Right Superior Isolated/Blocked='Yes', Right Inferior Isolated/Blocked='Yes')] / COUNT of [(Left Superior Isolated/Blocked in (Yes, No) , Left Inferior Isolated/Blocked in (Yes, No), Left Common Ostium Isolated/Blocked in (Yes, No), Right Middle Isolated/Blocked in (Yes, No), Right Superior Isolated/Blocked in (Yes, No), Right Inferior Isolated/Blocked in (Yes, No))] **in Procedural data form (PR)**
- Derived criteria "Proportion of all ablated pulmonary veins isolated using the study device during the Index Procedure that remain isolated at the 75-day remapping procedure" will be defined as follows:
(Derived criteria "Total number of veins isolated" - Derived criteria "Number of veins with gaps")/ Derived criteria "Total number of veins isolated"
- Derived criteria Proportion "Chronic CTI at 75d remap" will be defined as follows:
IF CTI lesion durable ='Yes' **in Follow-up 3D electroanatomical mapping form (RM)** **THEN** Chronic CTI at 75d remap ='Yes'
ELSE IF CTI lesion durable ='No' **in Follow-up 3D electroanatomical mapping form (RM)** **THEN** Chronic CTI at 75d remap ='No'
- Derived criteria Proportion "LAPW chronic isolation" will be defined as follows:
IF Anatomical Structure/Area other specification 1 **IN** ("POSTERIOR WALL" "LA POSTERIOR WALL" "LAPW" "PA WALL" "BOX POSTERIOR WALL") **AND** Other 1 Lesion durable = 'yes' **OR** Anatomical Structure/Area other specification 2 **IN** ("POSTERIOR WALL" "LA POSTERIOR WALL" "LAPW" "PA WALL" "BOX POSTERIOR WALL") **AND** Other 2 Lesion durable = ='Yes' **in Follow-up 3D electroanatomical mapping form (RM)** **THEN** LAPW chronic isolation= 'Yes'

CONFIDENTIEL / CONFIDENTIAL

Toute reproduction ou distribution, totale ou partielle, de ce document, sans autorisation préalable de ICON PLC est interdite.
Reproduction and distribution of this document, in whole or in part, is strictly forbidden without prior authorization from ICON PLC.

	STATISTICAL ANALYSIS PLAN	FARAPULSE PersAFOne SAP V1.0 PERSAFONE Page 26 /49
---	----------------------------------	--

ELSE LAPW chronic isolation = 'No'

Primary Safety endpoint

Unless otherwise indicated, all the following variables will be derived from the Adverse event adjudication form (CE)

- Derived criteria "Death" will be defined as follows:

IF (30≤ (EVENT DATE-PROCEDURE DATE IN **PROCEDURAL DATA FORM (PR)**) **OR** (30≤ (EVENT DATE-≤REMAPPING DATE IN **FOLLOW-UP 3D ELECTROANATOMICAL MAPPING FORM (RM)**) **AND** PRIMARY SAFETY ENDPOINT EVENT CRITERIA=' Death' **THEN** DEATH='Yes'
ELSE DEATH='No'

- Derived criteria "Myocardial infarction" will be defined as follows:

IF (30≤ (EVENT DATE-PROCEDURE DATE IN **PROCEDURAL DATA FORM (PR)**) **OR** (30≤ (EVENT DATE-REMAPPING DATE IN **FOLLOW-UP 3D ELECTROANATOMICAL MAPPING FORM (RM)**) **AND** PRIMARY SAFETY ENDPOINT EVENT CRITERIA=' Myocardial infarction' **THEN** Myocardial infarction='Yes'.

ELSE Myocardial infarction ='No'.

- Derived criteria "PV Stenosis" will be defined as follows:

IF (0≤ (EVENT DATE-PROCEDURE DATE IN **PROCEDURAL DATA FORM (PR)**) ≤360 **AND** PRIMARY SAFETY ENDPOINT EVENT CRITERIA=' PV Stenosis' **THEN** PV Stenosis ='Yes'.
ELSE PV Stenosis ='No'.

- Derived criteria "Diaphragmatic Paralysis" will be defined as follows:

IF (30≤ (EVENT DATE-PROCEDURE DATE IN **PROCEDURAL DATA FORM (PR)**) **OR** (30≤ (EVENT DATE-REMAPPING DATE IN **FOLLOW-UP 3D ELECTROANATOMICAL MAPPING FORM (RM)**) **AND** PRIMARY SAFETY ENDPOINT EVENT CRITERIA=' Diaphragmatic Paralysis' **THEN** Diaphragmatic Paralysis ='Yes'.
ELSE Diaphragmatic Paralysis ='No'.

- Derived criteria "AE fistula" will be defined as follows:

IF (0≤ (EVENT DATE-PROCEDURE DATE IN **PROCEDURAL DATA FORM (PR)**) ≤360 **AND** PRIMARY SAFETY ENDPOINT EVENT CRITERIA=' AE fistula' **THEN** AE fistula ='Yes'.
ELSE AE fistula ='No'.

- Derived criteria "TIA" will be defined as follows:

IF (30≤ (EVENT DATE-PROCEDURE DATE IN **PROCEDURAL DATA FORM (PR)**) **OR** (30≤ (EVENT DATE-REMAPPING DATE IN **FOLLOW-UP 3D ELECTROANATOMICAL MAPPING FORM (RM)**) **AND** PRIMARY SAFETY ENDPOINT EVENT CRITERIA=' TIA' **THEN** TIA=Yes.
ELSE TIA='No'.

- Derived criteria "CVA" will be defined as follows:

CONFIDENTIEL / CONFIDENTIAL

Toute reproduction ou distribution, totale ou partielle, de ce document, sans autorisation préalable de ICON PLC est interdite.
Reproduction and distribution of this document, in whole or in part, is strictly forbidden without prior authorization from ICON PLC.

	STATISTICAL ANALYSIS PLAN	FARAPULSE PersAFOne SAP V1.0 PERSAFONE Page 27 /49
---	----------------------------------	--

IF (30≤ (EVENT DATE-PROCEDURE DATE IN **PROCEDURAL DATA FORM (PR)**) **OR** (30≤ (EVENT DATE-REMAPPING DATE IN **FOLLOW-UP 3D ELECTROANATOMICAL MAPPING FORM (RM)**) **AND** PRIMARY SAFETY ENDPOINT EVENT CRITERIA=' CVA' **THEN** CVA='Yes'.
ELSE CVA='No'.

- Derived criteria "Major pericarditis" will be defined as follows:
IF (30≤ (EVENT DATE-PROCEDURE DATE IN **PROCEDURAL DATA FORM (PR)**) **OR** (30≤ (EVENT DATE-REMAPPING DATE IN **FOLLOW-UP 3D ELECTROANATOMICAL MAPPING FORM (RM)**) **AND** PRIMARY SAFETY ENDPOINT EVENT CRITERIA=' Major pericarditis' **THEN** Major pericarditis ='Yes'.
ELSE Major pericarditis ='No'.
- Derived criteria "Tamponade/Perforation" will be defined as follows:
IF (30≤ (EVENT DATE-PROCEDURE DATE IN **PROCEDURAL DATA FORM (PR)**) **OR** (30≤ (EVENT DATE-REMAPPING DATE IN **FOLLOW-UP 3D ELECTROANATOMICAL MAPPING FORM (RM)**) **AND** PRIMARY SAFETY ENDPOINT EVENT CRITERIA=' Tamponade/Perforation' **THEN** Tamponade/Perforation ='Yes'
ELSE Tamponade/Perforation ='No'.
- Derived criteria "Pneumothorax" will be defined as follows:
IF (30≤ (EVENT DATE-PROCEDURE DATE IN **PROCEDURAL DATA FORM (PR)**) **OR** (30≤ (EVENT DATE-REMAPPING DATE IN **FOLLOW-UP 3D ELECTROANATOMICAL MAPPING FORM (RM)**) **AND** PRIMARY SAFETY ENDPOINT EVENT CRITERIA=' Pneumothorax' **THEN** Pneumothorax ='Yes'
ELSE Pneumothorax ='No'
- Derived criteria "Heart Block" will be defined as follows:
IF (30≤ (EVENT DATE-PROCEDURE DATE IN **PROCEDURAL DATA FORM (PR)**) **OR** (30≤ (EVENT DATE-REMAPPING DATE IN **FOLLOW-UP 3D ELECTROANATOMICAL MAPPING FORM (RM)**) **AND** PRIMARY SAFETY ENDPOINT EVENT CRITERIA=' Heart Block' **THEN** Heart Block ='Yes'
ELSE Heart Block ='No'
- Derived criteria "Pulmonary Edema" will be defined as follows:
IF (30≤ (EVENT DATE-PROCEDURE DATE IN **PROCEDURAL DATA FORM (PR)**) **OR** (30≤ (EVENT DATE-REMAPPING DATE IN **FOLLOW-UP 3D ELECTROANATOMICAL MAPPING FORM (RM)**) **AND** PRIMARY SAFETY ENDPOINT EVENT CRITERIA=' Pulmonary Edema' **THEN** Pulmonary Edema ='Yes'
ELSE Pulmonary Edema ='No'
- Derived criteria "New or Prolonged Hospitalization, excl. AF/AFL" will be defined as follows:
IF (30≤ (EVENT DATE-PROCEDURE DATE IN **PROCEDURAL DATA FORM (PR)**) **OR** (30≤ (EVENT DATE-REMAPPING DATE IN **FOLLOW-UP 3D ELECTROANATOMICAL MAPPING FORM (RM)**) **AND** PRIMARY SAFETY ENDPOINT EVENT CRITERIA=' New or Prolonged Hospitalization, excl. AF/AFL' **THEN** New or Prolonged Hospitalization, excl. AF/AFL ='Yes'
ELSE New or Prolonged Hospitalization, excl. AF/AFL ='No'

CONFIDENTIEL / CONFIDENTIAL

Toute reproduction ou distribution, totale ou partielle, de ce document, sans autorisation préalable de ICON PLC est interdite.
Reproduction and distribution of this document, in whole or in part, is strictly forbidden without prior authorization from ICON PLC.

	STATISTICAL ANALYSIS PLAN	FARAPULSE PersAFOne SAP V1.0 PERSAFONE Page 28 /49
---	----------------------------------	--

- Derived criteria “Vascular Access Complication” will be defined as follows:
IF (30≤ (EVENT DATE-PROCEDURE DATE IN PROCEDURAL DATA FORM (PR)) **OR** (30≤ (EVENT DATE-REMAPPING DATE IN FOLLOW-UP 3D ELECTROANATOMICAL MAPPING FORM (RM)) **AND** PRIMARY SAFETY ENDPOINT EVENT CRITERIA=’ Vascular Access Complication’ **THEN** Vascular Access Complication =’Yes’
ELSE Vascular Access Complication =’No’
- Derived criteria “Total Early and Late Onset Composite Safety Endpoint” will be defined as follows:
IF Death=Yes **OR** Myocardial infarction =Yes **OR** PV Stenosis =Yes **OR** Diaphragmatic Paralysis =Yes **OR** AE fistula =Yes **OR** TIA =Yes **OR** CVA=Yes **OR** Major pericarditis =Yes **OR** Tamponade/Perforation =Yes **OR** Pneumothorax =Yes **OR** Heart Block =Yes **OR** Pulmonary Edema =Yes **OR** New or Prolonged Hospitalization, excl. AF/AFL =Yes **OR** Vascular Access Complication =Yes **THEN** Total Early and Late Onset Composite Safety Endpoint =’Yes’
ELSE Total Early and Late Onset Composite Safety Endpoint =’No’
- Derived criteria “Total Early Onset Composite Safety Endpoint” will be defined as follows:
IF Death=Yes **OR** Myocardial infarction =Yes **OR** Diaphragmatic Paralysis =Yes **OR** TIA =Yes **OR** CVA=Yes **OR** Major pericarditis =Yes **OR** Tamponade/Perforation =Yes **OR** Heart Block =Yes **OR** New or Prolonged Hospitalization, excl. AF/AFL =Yes **OR** Vascular Access Complication =Yes **THEN** Total Early Onset Composite Safety Endpoint=’Yes’
ELSE Total Early Onset Composite Safety Endpoint=’No’
- Derived criteria “Total Late (any time during follow-up through 12 months)” will be defined as follows:
IF PV Stenosis =Yes **OR** AE fistula =Yes **THEN** Total Late (any time during follow-up through 12 months) =’Yes’
ELSE Total Late (any time during follow-up through 12 months) =’No’.

Secondary Safety endpoint

- Derived criteria “Death 7 days” will be defined as follows:
IF (7≤ (EVENT DATE-PROCEDURE DATE IN PROCEDURAL DATA FORM (PR)) **OR** (7≤ (EVENT DATE-REMAPPING DATE IN FOLLOW-UP 3D ELECTROANATOMICAL MAPPING FORM (RM)) **AND** PRIMARY SAFETY ENDPOINT EVENT CRITERIA=’ Death’ **THEN** DEATH=’Yes’
ELSE DEATH=’No’
- Derived criteria “Myocardial infarction 7 days” will be defined as follows:
IF (7≤ (EVENT DATE-PROCEDURE DATE IN PROCEDURAL DATA FORM (PR)) **OR** (7≤ (EVENT DATE-REMAPPING DATE IN FOLLOW-UP 3D ELECTROANATOMICAL MAPPING FORM (RM)) **AND** PRIMARY SAFETY ENDPOINT EVENT CRITERIA=’ Myocardial infarction’ **THEN** Myocardial infarction=’Yes’.
ELSE Myocardial infarction = ‘No’.
- Derived criteria “Diaphragmatic Paralysis 7 days” will be defined as follows:

CONFIDENTIEL / CONFIDENTIAL

Toute reproduction ou distribution, totale ou partielle, de ce document, sans autorisation préalable de ICON PLC est interdite.
Reproduction and distribution of this document, in whole or in part, is strictly forbidden without prior authorization from ICON PLC.

	STATISTICAL ANALYSIS PLAN	FARAPULSE PersAFOne SAP V1.0 PERSAFONE Page 29 /49
---	----------------------------------	--

IF (7≤ (EVENT DATE-PROCEDURE DATE IN PROCEDURAL DATA FORM (PR)) **OR** (7≤ (EVENT DATE-REMAPPING DATE IN FOLLOW-UP 3D ELECTROANATOMICAL MAPPING FORM (RM)) **AND** PRIMARY SAFETY ENDPOINT EVENT CRITERIA=' Diaphragmatic Paralysis' **THEN** Diaphragmatic Paralysis ='Yes'.
ELSE Diaphragmatic Paralysis ='No'.

- Derived criteria "TIA 7 days" will be defined as follows:

IF (7≤ (EVENT DATE-PROCEDURE DATE IN PROCEDURAL DATA FORM (PR)) **OR** (7≤ (EVENT DATE-REMAPPING DATE IN FOLLOW-UP 3D ELECTROANATOMICAL MAPPING FORM (RM)) **AND** PRIMARY SAFETY ENDPOINT EVENT CRITERIA=' TIA' **THEN** TIA='Yes'.
ELSE TIA='No'.

- Derived criteria "CVA 7 days" will be defined as follows:

IF (7≤ (EVENT DATE-PROCEDURE DATE IN PROCEDURAL DATA FORM (PR)) **OR** (7≤ (EVENT DATE-REMAPPING DATE IN FOLLOW-UP 3D ELECTROANATOMICAL MAPPING FORM (RM)) **AND** PRIMARY SAFETY ENDPOINT EVENT CRITERIA=' CVA' **THEN** CVA='Yes'.
ELSE CVA='No'.

- Derived criteria "Major pericarditis 7 days" will be defined as follows:

IF (7≤ (EVENT DATE-PROCEDURE DATE IN PROCEDURAL DATA FORM (PR)) **OR** (7≤ (EVENT DATE-REMAPPING DATE IN FOLLOW-UP 3D ELECTROANATOMICAL MAPPING FORM (RM)) **AND** PRIMARY SAFETY ENDPOINT EVENT CRITERIA=' Major pericarditis' **THEN** Major pericarditis = 'Yes'.
ELSE Major pericarditis = 'No'.

- Derived criteria "Tamponade/Perforation 7 days" will be defined as follows:

IF (7≤ (EVENT DATE-PROCEDURE DATE IN PROCEDURAL DATA FORM (PR)) **OR** (7≤ (EVENT DATE-REMAPPING DATE IN FOLLOW-UP 3D ELECTROANATOMICAL MAPPING FORM (RM)) **AND** PRIMARY SAFETY ENDPOINT EVENT CRITERIA=' Tamponade/Perforation' **THEN** Tamponade/Perforation ='Yes'.
ELSE Tamponade/Perforation = 'No'.

- Derived criteria "Pneumothorax 7 days" will be defined as follows:

IF (7≤ (EVENT DATE-PROCEDURE DATE IN PROCEDURAL DATA FORM (PR)) **OR** (7≤ (EVENT DATE-REMAPPING DATE IN FOLLOW-UP 3D ELECTROANATOMICAL MAPPING FORM (RM)) **AND** PRIMARY SAFETY ENDPOINT EVENT CRITERIA=' Pneumothorax' **THEN** Pneumothorax ='Yes'. **ELSE** Pneumothorax = 'No'.

- Derived criteria "Heart Block 7 days" will be defined as follows:

IF (7≤ (EVENT DATE-PROCEDURE DATE IN PROCEDURAL DATA FORM (PR)) **OR** (7≤ (EVENT DATE-REMAPPING DATE IN FOLLOW-UP 3D ELECTROANATOMICAL MAPPING FORM (RM)) **AND** PRIMARY SAFETY ENDPOINT EVENT CRITERIA=' Heart Block' **THEN** Heart Block = 'Yes'.
ELSE Heart Block = 'No'.

- Derived criteria "Pulmonary Edema 7 days" will be defined as follows:

CONFIDENTIEL / CONFIDENTIAL

Toute reproduction ou distribution, totale ou partielle, de ce document, sans autorisation préalable de ICON PLC est interdite.
Reproduction and distribution of this document, in whole or in part, is strictly forbidden without prior authorization from ICON PLC.

	STATISTICAL ANALYSIS PLAN	FARAPULSE PersAFOne SAP V1.0 PERSAFONE Page 30 /49
---	----------------------------------	--

IF (7≤ (EVENT DATE-PROCEDURE DATE IN PROCEDURAL DATA FORM (PR)) **OR** (7≤ (EVENT DATE-REMAPPING DATE IN FOLLOW-UP 3D ELECTROANATOMICAL MAPPING FORM (RM)) **AND** PRIMARY SAFETY ENDPOINT EVENT CRITERIA=' Pulmonary Edema' **THEN** Pulmonary Edema = 'Yes'.
ELSE Pulmonary Edema = 'No'.

- Derived criteria "New or Prolonged Hospitalization, excl. AF/AFL 7 days" will be defined as follows:
IF (7≤ (EVENT DATE-PROCEDURE DATE IN PROCEDURAL DATA FORM (PR)) **OR** (7≤ (EVENT DATE-REMAPPING DATE IN FOLLOW-UP 3D ELECTROANATOMICAL MAPPING FORM (RM)) **AND** PRIMARY SAFETY ENDPOINT EVENT CRITERIA=' New or Prolonged Hospitalization, excl. AF/AFL' **THEN** New or Prolonged Hospitalization, excl. AF/AFL = 'Yes'.
ELSE New or Prolonged Hospitalization, excl. AF/AFL = 'No'.
- Derived criteria "Vascular Access Complication 7 days" will be defined as follows:
IF (7≤ (EVENT DATE-PROCEDURE DATE IN PROCEDURAL DATA FORM (PR)) **OR** (7≤ (EVENT DATE-REMAPPING DATE IN FOLLOW-UP 3D ELECTROANATOMICAL MAPPING FORM (RM)) **AND** PRIMARY SAFETY ENDPOINT EVENT CRITERIA=' Vascular Access Complication' **THEN** Vascular Access Complication = 'Yes'.
ELSE Vascular Access Complication = 'No'.
- Derived criteria "Total Early Onset Composite Safety Endpoint assessed at 7 days" will be defined as follows:
IF Death 7 days='Yes' **OR** Myocardial infarction 7 days='Yes' **OR** Diaphragmatic Paralysis 7 days='Yes' **OR** TIA 7 days='Yes' **OR** CVA 7 days='Yes' **OR** Major pericarditis 7 days='Yes' **OR** Tamponade/Perforation 7 days='Yes' **OR** Heart Block 7 days='Yes' **OR** New or Prolonged Hospitalization, excl. AF/AFL 7 days='Yes' **OR** Vascular Access Complication 7 days='Yes' **THEN** Total Early Onset Composite Safety Endpoint assessed at 7 days = 'Yes'.
ELSE Total Early Onset Composite Safety Endpoint assessed at 7 days = 'No'.
- Derived criteria "Device-Related Serious Adverse Events (SAEs)" will be defined as follows:
IF CEC seriousness ="Serious" **AND** CEC relationship to study Device in (Causal relationship, Probably related, Possibly related, Unlikely to be related) in adverse event adjudication form **THEN** Device-Related Serious Adverse Events (SAEs)='Yes'; **ELSE** Device-Related Serious Adverse Events (SAEs)='No'
- Derived criteria "Procedure-Related Serious Adverse Events (SAEs)" will be defined as follows:
IF CEC relationship to study procedure in (Causal relationship, Probably related, Possibly related, Unlikely to be related) **AND** CEC seriousness ='Serious' **THEN** Procedure-Related Serious Adverse Events (SAEs)='Yes'
ELSE IF CEC relationship to study procedure ='Not related' **AND** CEC seriousness =" Serious" **THEN** Procedure-Related Serious Adverse Events (SAEs)='No'
- Derived criteria "Cardioversion" will be defined as follows:
IF Arrhythmia-Treatment DC Cardioversion is ticked in **Arrhythmia episodes form** **THEN** Cardioversion ='Yes';
ELSE Cardioversion ='No'

CONFIDENTIEL / CONFIDENTIAL

Toute reproduction ou distribution, totale ou partielle, de ce document, sans autorisation préalable de ICON PLC est interdite.
Reproduction and distribution of this document, in whole or in part, is strictly forbidden without prior authorization from ICON PLC.

	STATISTICAL ANALYSIS PLAN	FARAPULSE PersAFOne SAP V1.0 PERSAFONE Page 31 /49
---	----------------------------------	--

- Derived criteria “Stroke after index procedure” will be defined as follows:
IF Event name='STROKE' in **Adverse event form** **AND** Event start date ≥ Procedure date in **Procedural data Form (PR)** **THEN** STROKE='Yes'
ELSE STROKE='No'
- Derived criteria “Transient Ischemic Attack (TIA) after index procedure” will be defined as follows:
IF Event name=' Transient Ischemic Attack' in **Adverse event form** **AND** Event start date ≥ Procedure date in **Procedural data Form (PR)** **THEN** TIA='Yes'
ELSE TIA='No'
- Derived criteria “Stroke after Remap procedure” will be defined as follows:
IF Event name='STROKE' in **Adverse event form** **AND** Event start date ≥ Remap date IN **FOLLOW-UP 3D ELECTROANATOMICAL MAPPING FORM (RM)** **THEN** STROKE='Yes'
ELSE STROKE='No'
- Derived criteria “Transient Ischemic Attack (TIA) after Remap procedure” will be defined as follows:
IF Event name=' Transient Ischemic Attack' in **Adverse event form** **AND** Event start date ≥ Remap date in **FOLLOW-UP 3D ELECTROANATOMICAL MAPPING FORM (RM)** **THEN** TIA='Yes'
ELSE TIA='No'
- Derived criteria “Arrhythmia-related (AF, AFL, AT) hospitalization” will be defined as follows:
IF Arrhythmia-related (AF, AFL, AT) hospitalization ='Yes' in **MDT excel file** **THEN** Arrhythmia-related (AF, AFL, AT) hospitalization ='Yes'
ELSE IF Arrhythmia-related (AF, AFL, AT) hospitalization ='No' in **MDT excel file** **THEN** Arrhythmia-related (AF, AFL, AT) hospitalization ='No'
- Derived criteria “Death” will be defined as follows:
IF SAE: Death='Yes' in **Adverse event form** **OR** Reason ='Patient death' in **study exit form** **THEN** Death='Yes'
ELSE Death='No'

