5.6 Populations for Analysis

Enrolled Population: all subjects who provided their informed consent.

Safety Subjects/Intent to Treat Subjects: all enrolled subjects except those who terminate their participation prior to the beginning of the Index Procedure.

Per Protocol Subjects: Intent-to-treat subjects for whom the Index Procedure is finished without interfering investigational device deficiency or malfunction.

Reasons for exclusion from the populations will be given, and a summary of adverse events for these subjects, if any, will be provided.

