7.4 Device Deficiencies

A Device Deficiency is an inadequacy of an investigational medical device related to its identity, quality, durability, reliability, safety or performance. This may include malfunctions, use error, or inadequacy in the information supplied by the manufacturer.

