2.3. Analysis Sets

2.3.1. Definition of patient populations

3 populations will be defined:

- The Enrolled population will include all subjects who provided their informed consent.
- The Safety / Intent-to-Treat (ITT) population will include all enrolled subjects except those who terminate their participation prior to the beginning of the Index Procedure.
- The Per Protocol (PP) population will include Intent-to-treat subjects for whom the Index Procedure is finished without interfering investigational device deficiency or malfunction.

The choice of reported analysis on ITT or PP populations will be driven by the purposes of the analysis.

In any case, the primary feasibility endpoint will be assessed on the ITT and PP populations.

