2.5. Derived Criteria Calculation

If at least one of the items needed to calculate a derived criteria is missing, then the corresponding derived criteria will be considered as missing.

Patient Disposition:

- Derived criteria “Enrolled population” will be analysed as:
IF the date of patient consent is filled in **Patient eligibility form (IE)** **THEN** “Enrolled population” = ‘Yes’
ELSE “Enrolled population” = ‘No’.
- Derived criteria “ITT population” will be defined as follows:
IF “Enrolled population” = ‘Yes’ in **Patient eligibility form (IE)** and the date of the Procedure is filled in **Procedural data form (PR)** **THEN** “ITT population” = ‘Yes’
ELSE “ITT population” = ‘No’.
- Derived criteria “Per Protocol population PP” will be defined as follows:
IF “ITT population” = ‘Yes’ **AND** Device Deficiency Number is not filled **AND** Serial # is not filled in **Device Deficiency DD Form** **THEN** Per Protocol population = ‘Yes’
ELSE Per Protocol population = ‘No’.
- Derived criteria “Time of patient follow-up” will be calculated as:
Date of study exit/withdrawal (*) in **Patient eligibility form (IE)** – date of procedure in **Procedural data form (PR)**
*if the patient is still in the study, the last visit date will be used instead of the exit/ withdrawal one.
- Derived criteria “COVID status” will be calculated as:
IF “Related to COVID-19 situation” =1 **OR** the term “COVID” exist in “reason for deviation” **AND** date of deviation is filled in **Protocol deviation form (PD)**, **THEN** CLASS=“ COVID-19”
ELSE IF date of deviation is filled **THEN** CLASS= “NOT COVID-19”.

Baseline Patient Characteristics:

- Derived criteria “Time from first AF diagnosis until consent date (months)” will be defined as follows:
Informed consent date – date of first documented AF diagnosis in **AF history form (AH)**.
- Derived criteria “Time between the most recent AF episode and the enrollment (months)” will be defined as follows:
Informed consent date – date of most recent AF episode in **AF history form (AH)**.
- Derived criteria “Permanent pacemaker or ICD” will be defined as follows:
IF Pacemaker, Implantable Cardioverter Defibrillator or Cardiac Resynchronization therapy device= ‘Yes’ in **Patient eligibility Form (IE)** **THEN** Permanent pacemaker or ICD=‘Yes’

CONFIDENTIEL / CONFIDENTIAL

Toute reproduction ou distribution, totale ou partielle, de ce document, sans autorisation préalable de ICON PLC est interdite.

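### The Per Protocol derivation in SAP 2.5 does not implement the definition: it ignores whether a deficiency interfered, which procedure it belonged to, and whether the Index Procedure was completed

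*SAP*

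**What the plan says.** Protocol 5.6 defines Per Protocol Subjects as "Intent-to-treat subjects for whom the Index Procedure is finished without interfering investigational device deficiency or malfunction". SAP 2.3.1 gives the same definition and uses PP, alongside ITT, for the primary feasibility endpoint. Table 9 reports Acute Procedural Success (APS) on ITT and Table 10 reports it on PP.

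SAP 2.5, under Patient Disposition, gives the rule to be programmed. A subject is PP if three things hold: ITT is Yes, "Device Deficiency Number is not filled", and "Serial # is not filled in" the Device Deficiency form. Everyone else is not PP. The ITT rule that feeds it needs only a consent date and that "the date of the Procedure is filled in" the procedural form.

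**The concern.** The definition carries three conditions: the procedure was finished, the deficiency interfered, and the deficiency belongs to the Index Procedure. The derivation contains none of them, and ITT does not supply them.

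The protocol's own data rules make the gap reachable:

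- Protocol 7.4 defines a deficiency broadly: "This may include malfunctions, use error, or inadequacy in the information supplied by the manufacturer".
- Protocol 7.8 sends deficiencies that neither contributed nor were likely to contribute to a serious adverse event to the same case report form.
- Protocol 3.12.5 collects deficiencies at the 75-day Remap as well as at the Index Procedure.

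The Remap case is the clearest fault. A deficiency about 75 days later would remove a subject from the analysis of an outcome settled on the day of the Index Procedure. What is at stake is the PP version of the primary feasibility result, and whether the reasons given for exclusion from PP agree with the definition.

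**Working it through.** The documents state no size or expected result for the PP set, so there is no figure to reproduce. The check is a comparison of two rules, followed by assumed illustrations.

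**Step 1. Compare the rules.** Defined PP = finished AND no interfering Index Procedure deficiency. Programmed PP = no deficiency number and no serial number on the deficiency form. All subjects below are ITT, and a deficiency record means one with either field filled.

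| Index Procedure | Deficiency record | Defined PP | Programmed PP |
|---|---|---|---|
| Finished | None | In | In |
| Finished | Index, interfering | Out | Out |
| Finished | Index, non-interfering | In | **Out** |
| Finished | Remap only | In | **Out** |
| Unfinished | None | Out | **In** |
| Unfinished | Index, interfering | Out | Out |
| Unfinished | Index, non-interfering | Out | Out |
| Unfinished | Remap only | Out | Out |

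The rules disagree in 3 of 8 cells. Two wrongly remove subjects and one wrongly keeps them.

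**Step 2. Interval method.** Under SAP 2.1.4, when the asymptotic assumptions fail, the interval is Agresti-Coull if the proportion is 0% or 100%, and exact otherwise. For x successes in n, with z = 1.96 and z² = 3.84, the Agresti-Coull lower limit is p̃ − z√(p̃(1 − p̃)/ñ), where ñ = n + z² and p̃ = (x + z²/2)/ñ.

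**Step 3. Base illustration (assumed).** 40 treated, all finished and successful, 4 with a deficiency record, 1 of the 4 interfering at the Index Procedure.

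- Programmed: n = 40 − 4 = 36, result 36/36. ñ = 39.84, p̃ = 37.92/39.84 = 0.952, lower limit 88.5%.
- Defined: n = 40 − 1 = 39, result 39/39. ñ = 42.84, p̃ = 40.92/42.84 = 0.955, lower limit 89.3%.

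The point estimate is 100% in both. The lower limit moves by 89.3 − 88.5 = 0.8 percentage points.

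**Step 4. Direction (assumed inputs, 40 treated).**

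- *Programmed rate lower.* Ten finished, successful subjects have only non-interfering or Remap records. Two have unfinished procedures, no record, and APS coded No. All others are finished and successful with no record. Defined: 38/38, 100% (89.1 to 100). Programmed: 28/30, 93.3% (exact 77.9 to 99.2).
- *Programmed rate higher.* All are finished. The only deficiency record is a non-interfering one in the only subject who failed. Defined: 39/40, 97.5% (exact 86.8 to 99.9). Programmed: 39/39, 100% (89.3 to 100).
- *No difference.* With no non-interfering or Remap-only record, and no unfinished procedure without a record, the two sets are identical.

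**The case against.** The strongest reply is that the consequences are limited. The study is descriptive with no hypothesis test (Protocol 5.3, SAP 2.2), APS is also reported on ITT, and the sets differ only if particular records or unfinished procedures occur. SAP 2.4.1.1 tabulates reasons for non-inclusion, and Listings 1 and 15 show exclusions and deficiencies by subject, so a careful reader could see what happened. If an unfinished procedure is coded as an APS failure, keeping it in PP lowers the rate, which is conservative. The programmed rule is also objective, whereas neither document says what makes a deficiency interfering. All of this stands as a limit on size. None of it makes the derivation match the definition, and the listings do not correct Table 10.

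Three stronger readings are tempting, and the documents do not support them.

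- *That the plan leaves open which set will be reported for APS.* SAP 2.3.1 does say "The choice of reported analysis on ITT or PP populations will be driven by the purposes of the analysis", but its next sentence commits the primary feasibility endpoint to both sets, and Tables 9 and 10 fix this. With no test to pass or fail, naming ITT as primary is a reasonable preference, not the correction of an error.
- *That the program makes PP look better than ITT by discarding device failures.* If the one interfering case in the base illustration were the only failure, PP would show 100% and ITT 39/40 = 97.5%. PP would show 100% under either rule (36/36 or 39/39), so that contrast comes from the definition.
- *That nobody can be PP*, because SAP 2.5 opens by making a derived criterion missing when any needed item is missing, and PP requires two blank fields. The PP rule explicitly tests for blanks, so the sensible reading is that a blank there means no deficiency. A clarifying sentence would remove the doubt.

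**Conclusion.** The mismatch is certain from the text, and nothing elsewhere in either document repairs it. Its effect is conditional. Table 10 is computed on the wrong set only if at least one subject has a non-interfering or Remap-only deficiency record, or an unfinished Index Procedure with no such record. In the base illustration the effect is 0.8 points on a descriptive lower limit, with the estimate unchanged. Less favourable assumptions move the estimate itself, in either direction. The counts of records and unfinished procedures, and the coding of an unfinished procedure as APS No, are assumptions. The case report form is not among the documents, so whether it already identifies the procedure or the effect of each deficiency cannot be seen. The rule should be corrected before analysis because it feeds one of the two reported results for the primary feasibility endpoint.

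**What to change.** Preferred route: in SAP 2.5, derive PP as ITT, AND Index Procedure completed, AND no deficiency dated at the Index Procedure and classed as interfering. Remap and non-interfering records are ignored. Three details are needed:

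- A written criterion for interfering, applied to each record before analysis and without reference to APS. The study is unblinded (Protocol 3.2), so a classification made with the outcome in view could select the set.
- A completion item. The procedural form already holds a procedure end time, which SAP 2.5 uses for procedure duration. An end time alone may not prove completion.
- A sentence saying that blank deficiency fields mean no deficiency, not a missing PP status.

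Alternative: if the broad, objective exclusion is what the sponsor wants, amend Protocol 5.6 and SAP 2.3.1 to say so, limit the rule to Index Procedure records, and either program the completion condition or drop it from the definition. This route also needs a protocol amendment under Protocol 10.4.

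The preferred route costs SAP wording, one program change, and classification of what should be a small number of deficiency records. No new subject assessments are needed.
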